### **11.2.4. Severity**

The severity of any AEs will be graded using the CTCAE vs 5.0 (see Annex 4). If the CTCAE has no code that matches, the following guide should be used:

Grade	Description
0	No adverse event
1	Mild; asymptomatic or mild symptoms; clinical or diagnostic observations only
2	Moderate; minimal, local or noninvasive intervention indicated
3	Severe or medically significant but not immediately life-threatening; hospitalization or prolongation of hospitalization indicated
4	Life-threatening consequences; urgent intervention indicated
5	Death related to adverse event

Grading of AEs is based on specific clinical criteria that will require evaluation by the study site Investigator. Should an AE stop and then restart, it will be considered two separate events and the severity assessed as described above.

## **11.3. Reporting procedures**

### **11.3.1. Reporting of adverse events (AEs)**

The investigator will try to obtain information about any adverse events that have occurred in all visits by examining or directly interrogating the patient. All information referring to adverse events must be recorded in the respective section of the CRF. AEs should be recorded according CTCAE v5.0. All adverse events that occur during the period comprehended from the start of study treatment to 30 days after last dose of the investigational products will be recorded. When one or more signs or symptoms correspond to a disease, the main diagnosis or syndrome will be notified. All adverse events will be followed until resolution or stabilization, or until it is determined that the study treatment or the patient's participation in the study has not been the cause. All adverse events still present at the end of the study period will be monitored until their final outcome is determined.

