## 1.9. Study design

This is an interventional, prospective, multicentric, single-arm, open label, phase IB clinical trial.

The following scheme depicts the basic trial design.

Patients diagnosed of metastatic or locally advanced non-curable TNBC that have received one or two treatment regimens for advanced disease will be candidates for the trial. A fresh tumor sample will be obtained in order to determine the phosphoproteomic profile of the tumor, preferably obtained after last treatment or the most recent sample as possible (from metastasis or first diagnosis according to sample availability) prior to study inclusion. If the patient has not a tumor sample available prior to study inclusion, the patient will not be allowed to participate in the study. Activation of the two kinases of interest will be determined centrally at CNIO. Only patients with scores above the upper quartile of at least one of them will be candidates. It is expected that approximately 40% of patients are positive for CDK4/6 and/or ERK.

Patients will then start treatment with continuous oral binimetinib and palbociclib 21 days on / 7days off, until disease progression. Tumor evaluation will be performed every 8 weeks. Study treatment will continue until disease progression, unacceptable toxicity, intercurrent serious disease, consent withdrawal or investigator's decision.

The study will be conducted at 8 Spanish sites and will enroll 25 patients.

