7. Alkaline phosphatase, aspartate aminotransferase (AST), alanine aminotransferase (ALT), $\gamma$ -glutamyltransferase (GGT), total bilirubin; blood urea/blood urea nitrogen (BUN), creatinine: creatinine clearance; glucose, albumin, cholesterol, triglyceride, phosphorus, lactate dehydrogenase (LDH), total protein, uric acid, creatinine phosphokinase (CPK); Sodium, potassium, calcium, magnesium, chloride, bicarbonate (HCO3). Biochemistry will be performed in the 14 days previous to start study treatment.
8. Free T3 and free T4 will only be measured if TSH is abnormal. They should also be measured if there is clinical suspicion of an adverse event related to the endocrine system. In the 14 days previous to start study treatment.
9. Urinalysis: bilirubin, blood, glucose, ketones, PH, protein specific gravity, colour and appearance. Dipstick test every cycle. Additional analyses will be done at investigator criteria in case of abnormal results. Urinalysis will be performed in the 14 days previous to start study treatment.
10. Coagulation tests: prothrombin time, APTT and INR. In the 14 days previous to start study treatment.
11. Serology: hepatitis B surface antigen, hepatitis C antibody, HIV antibody. In the 14 days previous to start study treatment and if clinically indicated thereafter.
12. Serum pregnancy test only pre-menopausal female subjects of childbearing potential. At study entry, every 4 weeks during the study treatment and at the end of study treatment.
13. All formalin-fixed, paraffin-embedded (FFPE) tissue samples block and one hematoxylin and eosin (H&E) stained tumor slide, both obtained in the 15 days before patient inclusion in the study, will be sent to CNIO in order to determine positivity of ERK and/or CDK4/6, preferably obtained after last treatment or the most recent sample as possible (from metastatic site or first diagnosis according to sample availability).
14. Tumor evaluation will be performed every 8 weeks until confirmed PD.
15. 21 days-on/7 days-off.
16. This applies to all non-serious AEs and SAEs that occur at any time during the administration of the study drug and up to 30 days after end of treatment.
17. Concurrent medications administered within the 28 days preceding day 1.
18. Blood sample: two CPT tubes of 7 ml will be obtained at baseline visit before treatment administration, at C2D1 and at disease progression (a 2 weeks window is allowed from confirmation of disease progression).

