### **10.3. End of treatment / early withdrawal**

The following procedures will be performed at end of treatment / early withdrawal visit:

- Tumor evaluation: PET-CT, CT and/or MRI, if patient stops study treatment for any reason other than disease progression
- Physical examination
- Ophthalmological examination
- Weight
- Vital Signs
- ECOG performance status
- 12-lead ECG: if clinically indicated
- ECHO/MUGA

- Hematology
- Biochemistry
- Serology
- TSH, fT3 y fT4
- Coagulation
- Urinalysis
- Pregnancy test
- Adverse events
- Concomitant medications
- Blood sample: two CPT tubes of 7 ml will be obtained at disease progression (a 2 weeks window is allowed from confirmation of disease progression).
- An image-guided biopsy will be done upon progression. The biopsy is allowed within 4 weeks after the confirmation of disease progression and in any case before starting the next line of treatment.

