### **11.1. Definitions**

#### **11.1.1. Adverse event (AE)**

An AE is any undesired experience that occurs in a patient participating in clinical research that is associated in time with the use of a medicinal product, whether or not it is considered to be related to the investigational products. Therefore, an adverse event can be any unintentional unfavorable sign (including an anomalous laboratory result), symptom or disease that is associated in time with the use of a medicinal product, whether or not it is considered to be related to the product. Pre-existing diseases that worsen during the study shall be notified as Adverse Events.

AEs include pre- or post-treatment events that occur as a result of study procedures (e.g. invasive procedures or modification of the patient's previous medication).

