### 11.3.2. Reporting of serious adverse events (SAEs)

The investigator will notify CRO of all serious adverse events that occur during the period comprehended from the start of study treatment to 30 days after last dose within 24 h of receiving knowledge of the same or, at the latest, on the next working day.

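### The AE definition covers harm from study procedures before treatment, but AE recording and SAE notification start at first dose, so a complication of a fresh screening biopsy has no reporting route

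*Protocol*

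**What the plan says.** **Definition.** Protocol 11.1.1 states that "AEs include pre- or post-treatment events that occur as a result of study procedures", and gives invasive procedures as an example.

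**Recording and notification.** Section 11.3.1 records "All adverse events that occur during the period comprehended from the start of study treatment to 30 days after last dose". Section 11.3.2 has the investigator notify the CRO of "all serious adverse events that occur during the period comprehended from the start of study treatment to 30 days after last dose". Footnote 16 of the study schedule (section 10) covers events "at any time during the administration of the study drug and up to 30 days after end of treatment".

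**Screening tissue.** Sections 1.9 and 6.1 say "A fresh tumor sample will be obtained in order to determine the phosphoproteomic profile of the tumor". The schedule row names both archival and fresh biopsy, and footnote 13 asks for material obtained in the 15 days before inclusion. The same sections, inclusion criterion 5 and section 10.1 also accept the most recent available sample, even one from first diagnosis.

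**Progression tissue.** Section 10.3 and footnote 19 require an image-guided biopsy on progression: "The biopsy is allowed within 4 weeks after the confirmation of disease progression".

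**Later contact.** Section 10.4 lists adverse events among the procedures at the safety visits 30 days and 6 months after the last dose.

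**The concern.** The protocol names a class of event, procedure-related harm before or after treatment, and then sets a collection window that cannot contain the pre-treatment part of it. A site could follow 11.3.1 and 11.3.2 to the letter and never tell the sponsor about a serious complication of tissue sampling done for the trial. The patients least protected are those tested, found biomarker-negative and never dosed. They take on the risk of any new sampling and have no other safety follow-up in the trial.

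What is at stake is oversight of harm from trial procedures. It is not the estimate of drug toxicity.

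**Working it through.** The plan gives no figure for this point, so the check compares the text and then counts patients and days.

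**1. Screening: is there any route for a pre-dose event?**
- Sections 11.3.1 and 11.3.2 open the window at start of treatment, and footnote 16 at drug administration. Days of capture before first dose: 0.
- The screening procedures in section 10.1 do not list adverse events.
- Section 13.5 asks for minimum eCRF data on screen failures, such as demographics and consent date, and the reason for failing. AEs are not named.
- Section 11.3.2 makes at least one suspect drug, with dose and dates, a mandatory element of a report. An undosed patient cannot supply it.
- Section 11.3.5 (events after the study) requires notification only when the event is considered related to study drug.
- The safety populations in Protocol 12.3 and SAP 5.1 both require at least one dose.

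None of these provisions supplies a route.

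**2. How many never-dosed patients could be affected?**

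Inputs: 25 patients to enrol (6.1); positivity about 40% (1.9, 6.1) or 42% (5.2).

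Number tested = 25 / positivity, rounded up. Never dosed = number tested − 25.

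| Positivity | 25 / positivity | Tested | Biomarker-negative, never dosed |
|---|---|---|---|
| 40% | 62.5 | 63 | 38 |
| 42% | 59.5 | 60 | 35 |

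This assumes that every biomarker-positive patient enrols. The share who need a new sample is not stated. If it is none, 0 are exposed; if it is all, about 35 to 38 are. Patients who do go on to treatment are also uncovered between a fresh biopsy and first dose.

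**3. Progression: does the biopsy fall inside the window?**

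Let g be the days from last dose to confirmed progression, and d the biopsy delay, from 0 to 28 days (4 weeks). The biopsy falls on day g + d after last dose and is inside the window if g + d ≤ 30. Of the 29 permitted days, the number inside is min(28, 30 − g) + 1 for g ≤ 30, and 0 for larger g.

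| g (days, assumed) | Permitted biopsy days inside | Capture left after the latest permitted biopsy |
|---|---|---|
| 0 | 29 of 29 | 2 days |
| 2 | 29 of 29 | 0 days |
| 7 | 24 of 29 | none; biopsy on day 35 |
| 14 | 17 of 29 | none; biopsy on day 42 |
| 28 | 3 of 29 | none; biopsy on day 56 |
| 31 | 0 of 29 | none; biopsy on day 59 |

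The documents give no distribution for g. Treatment runs to progression unless it stops earlier for toxicity or another reason (9.2), so small values should be usual. Section 8.1 tolerates toxicity interruptions of up to 28 days, and a patient who stops for toxicity may progress later still, so larger values can occur.

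**4. When does collection end?** Sections 11.3.1 and 11.3.2 say 30 days after last dose. Section 10.4 lists adverse events at a visit 6 months after it. The two do not agree.

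**The case against.** The case for leaving the plan alone has four parts.

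- **Existing tissue is accepted.** Many patients may need no new biopsy for the trial. This stands. It makes 35 to 38 an upper bound on never-dosed patients exposed. A reader might take it as the number of unrecorded biopsies, but the documents do not support that, because they do not say how many need fresh tissue. Footnote 13 and the design sections do show that fresh biopsies are foreseen.
- **Progression biopsies are largely covered.** This also stands. A reader might infer that complications of these biopsies generally go unrecorded, or that all 25 patients are exposed. That would require every patient to stop drug well before progression, and nothing in the documents says so. With the last dose 0 to 2 days before confirmed progression, every permitted biopsy day is inside the window.
- **AEs are sought at all visits (11.3.1) and listed at 6 months (10.4).** After treatment, this makes the end of collection inconsistent; it is not a clear omission. It gives no help before first dose or in undosed patients.
- **The safety objective concerns the drug combination, and the safety populations are dosed patients.** No endpoint or planned safety estimate changes. This limits the consequence to safety oversight, but does not remove the conflict with the protocol's own definition of an AE.

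**Conclusion.** The conflict is real for the screening biopsy. A complication that starts before first dose meets the definition in 11.1.1, yet no section provides for recording it or notifying it as serious, whether or not the patient is later treated.

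Among biomarker-negative, never-dosed patients, between 0 and about 35 to 38 could be exposed. That range rests on 40% to 42% positivity, full enrolment of 25, no other screening losses and an unknown share needing new tissue. It counts patients exposed to sampling, not complications; the documents give no complication rate.

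For the progression biopsy the gap is residual: patients who stopped drug well before progression, biopsies done late after an interval off drug, and complications that begin late. The 6-month AE item and the 30-day limit must also be reconciled. The point should be corrected because serious harm from a trial procedure could go unreported under the rule as written.

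**What to change.** 1. In 11.3.1, 11.3.2 and schedule footnote 16, record AEs and notify SAEs related to study procedures from the first (biomarker-testing) consent, screen failures included.
2. Continue this for a stated period after the progression biopsy. Ending at the biopsy itself would miss its complications.
3. Keep the existing window for all other events.
4. List procedure-related events separately from treatment-emergent AEs. The relationship field in the SAP's SAE listing (9.4) already has a category that includes procedures.
5. Align the sections that would otherwise block the change: the 6-month AE item in 10.4, the mandatory suspect drug in 11.3.2, and the screen-failure eCRF data in 13.5.

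The cost is protocol wording, an eCRF change that reaches screen failures, one extra listing and a small amount of additional reporting. No endpoint, sample size or analysis population changes.

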### 11.3.2. Reporting of serious adverse events (SAEs)

The investigator will notify CRO of all serious adverse events that occur during the period comprehended from the start of study treatment to 30 days after last dose within 24 h of receiving knowledge of the same or, at the latest, on the next working day.

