### **11.3.7. Pregnancy**

The investigator must report all pregnancies during the study, including follow up outcomes, within 24 hours of awareness.

Each pregnancy must be reported on a Pregnancy Report Form within 24 hours of becoming aware of the pregnancy. Pregnancy is not an AE, and therefore does not need to be reported as an AE unless there is a suspicion that the study drug may have interfered with the effectiveness of a contraceptive medication.

Any SAE that occurs during pregnancy must be recorded on the Pregnancy Report Form, reported as an SAE on the SAE Report Form (e.g., maternal serious complications, therapeutic abortion, ectopic pregnancy, stillbirth, neonatal death, congenital anomaly, birth defect) and reported to the Sponsor within 24 hours. Hospitalization for normal delivery of a healthy newborn should not be considered an SAE.

Any exposure during breast feeding must also be reported.

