### **11.3.8. Special Situations: Abuse, Misuse, Medication Errors, Overdose, and Accidental or Occupational Exposure**

- Abuse: is the persistent or sporadic, intentional excessive use of the study treatment which is accompanied by harmful physical or psychological effects.
- Misuse: medicinal product is intentionally and inappropriately used not in accordance with the authorized/approved product information.
- Medication error: is any preventable incident that may cause or lead to inappropriate study treatment use or patient harm while the study treatment is in the control of the health care professionals or patients. Such incident may be due to health care professional practice, product labeling, packaging and preparation, procedures for administration, and systems, including the following: prescribing, order communication, nomenclature, compounding, dispensing, distribution, administration, education, monitoring, and use.
- Overdose: is a deliberate or accidental administration of study treatment to a study patient, at a dose greater than that which was assigned to that patient per the study protocol and under the direction of the Investigator. Study investigator should be notified of overdose immediately, and the patient should be observed closely for AEs. Associated AEs should be treated and monitored by the Investigator.
- Accidental /Occupational exposure: is the unintentional exposure to a study treatment as a result of one's professional or non-professional occupation, or accidental exposure to a non-professional to whom exposure was not intended (i.e., study product given to wrong patient).

Reporting Special Situations: All occurrences of abuse, misuse, medication error, overdose, and accidental or occupational exposure of study treatment must be reported on a Serious Adverse Event Report Form to the Sponsor within 24 hours of awareness regardless of whether or not an AE or SAE has occurred. If the abuse, misuse, medication error, overdose, or accidental / occupational exposure is associated with an AE, an SAE Report Form must also be submitted to the Sponsor within 24 hours of awareness.

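### Protocol 11.3.2 lets an ordinary SAE wait for the next working day, while 11.3.7 and 11.3.8 require pregnancies and harmless overdoses to be reported within 24 hours

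*Protocol*

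**What the plan says.** Protocol section 11.3 sets separate time limits for different kinds of report.

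- **Ordinary SAEs (11.3.2).** From the start of treatment until 30 days after the last dose, the investigator notifies the CRO "within 24 h of receiving knowledge of the same or, at the latest, on the next working day".
- **Pregnancy (11.3.7).** "The investigator must report all pregnancies during the study, including follow up outcomes, within 24 hours of awareness". The section repeats the limit for the form: "Each pregnancy must be reported on a Pregnancy Report Form within 24 hours of becoming aware of the pregnancy". An SAE during pregnancy goes on both the pregnancy form and the SAE form, "and reported to the Sponsor within 24 hours".
- **Special situations (11.3.8).** Abuse, misuse, medication error, overdose and accidental exposure are reported on an SAE form "to the Sponsor within 24 hours of awareness regardless of whether or not an AE or SAE has occurred". If an adverse event is associated, "an SAE Report Form must also be submitted to the Sponsor within 24 hours of awareness".

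Only 11.3.2 mentions working days, and the protocol does not define the term. The recipient also differs. SAEs under 11.3.2 go to the CRO, with a safety-department e-mail address given directly below. SAEs in pregnancy and special situations go to the Sponsor. The SAP lists and tabulates SAEs (section 9.4) but says nothing about when they are notified.

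**The concern.** The limits run against the seriousness of the events. A site that follows the text may hold a fatal SAE over a weekend, but must report an overdose without consequences within 24 hours, weekend included. The protocol gives no reason for treating the two differently.

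What is at stake is how soon those running the trial learn of a serious toxicity. The trial combines two drugs at 8 sites. Protocol 5.2 expects some of their toxicities to overlap, and 11.3.6 calls knowledge of binimetinib's adverse events limited. The documents as supplied describe no trial-level safety committee or pausing rule. Individual SAE notification is therefore the documented route by which the CRO and sponsor hear of such an event and can inform other sites.

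**Working it through.** The plan gives no figure to reproduce. The check compares the sections and then applies calendar arithmetic.

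**Which limit binds.** In 11.3.2 the words 'at the latest' attach to the working-day alternative, so where the two limits differ the later one governs. Sections 11.3.7 and 11.3.8 have no such alternative. Nothing else in section 11.3, or in the SAP, returns ordinary SAEs to 24 hours.

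**Inputs.** The limit in 11.3.2; the 24-hour limit in 11.3.7 and 11.3.8; and, as an assumption, a Monday-to-Friday working week without a public holiday.

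**Formula.** Hours from awareness to report = 24 × (calendar days to the next working day) + clock time of report − clock time of awareness.

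- Friday 17:00 to Monday 17:00: 24 × 3 + 17 − 17 = 72 h.
- Friday 09:00 to Monday 17:00: 24 × 3 + 17 − 9 = 80 h.
- Saturday 17:00 to Monday 17:00: 24 × 2 + 17 − 17 = 48 h.
- Saturday 09:00 to Monday 17:00: 24 × 2 + 17 − 9 = 56 h.

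The result depends on the hour of awareness and on when the working day is taken to end:

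| Awareness | Next working day, 09:00 | 17:00 | 24:00 |
|---|---|---|---|
| Friday 09:00 | 72 h | 80 h | 87 h |
| Friday 17:00 | 64 h | 72 h | 79 h |
| Saturday 09:00 | 48 h | 56 h | 63 h |
| Saturday 17:00 | 40 h | 48 h | 55 h |
| Sunday 09:00 | 24 h | 32 h | 39 h |
| Monday to Thursday 09:00 | 24 h | 32 h | 39 h |
| Monday to Thursday 17:00 | 16 h | 24 h | 31 h |

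Over all hours of awareness on a Friday, with the report sent between 09:00 and 24:00 on Monday, the range is 57 to 96 h. A Saturday reaches 72 h only at the extreme, from 00:00 Saturday to 24:00 Monday. If Monday is a holiday, Friday 17:00 to Tuesday 17:00 is 24 × 4 = 96 h, and Friday 09:00 to the end of Tuesday is 96 + 24 − 9 = 111 h.

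**After the change.** With a plain 24-hour limit the maximum is 24 h on every day of the week.

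**The case against.** The best defence is that the clause is ordinary weekend practicality, that most sites will report sooner, and that patient safety does not hang on it. Part of this stands. During the first two cycles patients are seen weekly with haematology and biochemistry (Protocol 10, 10.2). The dose-adjustment rules (9.3) and withdrawal criteria (8.1) work at the site without waiting for the CRO. Section 11.3.3 separately binds the sponsor to legal time limits for suspected unexpected serious adverse reactions. It would therefore be too much to say that a weekend delay leaves other patients unprotected. The practicality argument is weaker, because 11.3.7 and 11.3.8 already require weekend reporting for matters that may involve no harm.

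Several stronger readings are tempting but lack support:

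- **That the rules cannot both be followed.** A reader might infer this for an SAE in pregnancy, or one linked to an overdose. But a report within 24 hours also meets the deadline in 11.3.2. What is left unsettled there is the recipient, CRO or Sponsor. The gap in timing is confined to ordinary SAEs.
- **That 72 hours applies to Saturday too.** Daytime awareness on a Saturday gives about 48 to 63 h in most cases.
- **That a share of days or a number of patients can be stated.** A reader might count Friday and Saturday as two days in seven and multiply by the SAE rates in Protocol 5.1.3.5. The day count depends on the clock time chosen: with awareness at 09:00 and a report at 17:00, every day exceeds 24 h. The rates are for binimetinib alone, in other tumours and partly at another dose. Nothing shows that awareness is spread evenly over the week.
- **That one safety mailbox already receives all these reports.** The documents do not say so, nor that any mailbox is staffed at weekends.

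**Conclusion.** The concern holds as an inconsistency within the protocol's own safety-reporting rules. An ordinary SAE, fatal or not, has a looser limit than a pregnancy or an overdose without harm. Deaths from disease progression are outside this statement, since 11.1.3 does not count them as SAEs. On an assumed Monday-to-Friday week, the permitted interval is about 72 h from a Friday and about 48 h or more from a Saturday, and longer with a Monday holiday. These are intervals that the wording allows, not delays shown to occur. The inconsistency itself does not depend on the assumed week or clock times; only the hours do. It rests on the protocol's text alone and touches no endpoint, estimate or sample size. It should be corrected because it concerns the notification of serious events and the remedy is small.

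**What to change.** In 11.3.2, delete the alternative that permits notification "on the next working day", so that every SAE carries the limit of 24 hours from awareness already used in 11.3.7 and 11.3.8. Add a sentence to 11.3: where one event falls under more than one of these sections, a single report within 24 hours, with whichever forms apply and sent to one named recipient, satisfies all of them. Name that recipient in all three sections.

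The cost is one deleted clause, one added sentence and occasional weekend form completion by sites, which 11.3.7 and 11.3.8 already require of them. The change governs when the site sends the report. The documents do not say who reads reports at weekends, so the sponsor should confirm that cover when naming the recipient.
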